2.0 HYPOTHESIS

CSF and plasma LZD PK exposure parameters will be lower when administered with high dose compared with standard dose RIF.

2.1 PRIMARY OBJECTIVE

To determine the CSF and plasma PK of LZD 1200 mg daily in TBM patients receiving high or standard dose RIF.

2.2 PRIMARY ENDPOINTS

CSF and plasma LZD PK parameters, including CSF to plasma ratio, rate of CSF uptake, and plasma absorption rate constant (k_a), drug clearance (CI/F), volume of distribution (V_d).

2.3 SECONDARY OBJECTIVE

1. To evaluate the safety and tolerability of 4 weeks of LZD 1200 mg for the treatment of TBM.

2. To determine if LZD exposures in the CSF and plasma predict linezolid AEs.

3. To compare longitudinal neurocognitive and functional outcomes in participants randomized to linezolid versus no LZD for the treatment of TBM.

4. To determine if LZD exposures in CSF and plasma predict neurocognitive and functional outcomes.

2.4 SECONDARY ENDPOINTS

1. Proportion of participants with Grade 3 or higher AEs at 4 weeks

2. Proportion of participants who complete LZD treatment

3. Exposure-response (PK-PD) relationship, with LZD as predictor and Grade 3 or higher AE as outcome variable

4. Modified Rankin Scale (death, severe disability, moderately severe, moderate disability, slight disability, no significant disability, no symptoms) at 12 and 24 weeks

5. Montreal Cognitive Assessment (MoCA) or neurocognitive battery performance at 12 and 24 weeks

6. Exposure-response (PK-PD) relationship, with linezolid as predictor and Modified Rankin Scale as outcome variable

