7.0 ADVERSE EVENTS AND STUDY MONITORING

7.1 Definition of Adverse Events

An adverse event (AE) is any unfavorable and unintended sign (including an abnormal laboratory finding), symptom, or diagnosis that occurs in a study participant during the conduct of the study REGARDLESS of the attribution (i.e., relationship of event to medical treatment/study product/device or procedure/intervention). This includes any occurrence that is new in onset or aggravated in severity or frequency from the baseline condition.

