7.2 Adverse Event Collection Requirements for this Study

All AEs must be recorded on the CRFs if any of the following criteria have been met.

- All Grade 3 to 5 AEs
- All AEs that led to a change in study treatment/intervention regardless of grade
- All AEs meeting serious adverse event definition or expedited adverse event reporting requirement

All AEs that are reported must have their severity graded. AEs will be graded according to the Division of AIDS Table for Grading the Severity of Adult and Pediatric Adverse Events (DAIDS AE Grading Table), Corrected Version 2.1, July 2017, which can be found on the DAIDS RSC website at https://rsc.niaid.nih.gov/clinical-research-sites/daids-adverse-event-grading-tables

Serious Adverse Events (SAEs)

A SAE is defined as any untoward medical occurrence that:

- Results in death
- Is life-threatening
- Requires inpatient hospitalization or prolongation of existing hospitalization
- Results in persistent or significant disability/incapacity
- Is a congenital anomaly/birth defect
- Is an important medical event that may not be immediately life-threatening or result in death or hospitalization but may jeopardize the patient or may require intervention to prevent one of the other outcomes listed in the definition above.

All pre-existing conditions present at study entry **must be clearly documented on the CRF at entry.** If the frequency, intensity, or the character of the condition worsens to Grade 3 to 5 level during the reporting period, the event should be defined as an AE.

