7.4 Expected disease-related events

This study population, with TB and advanced HIV, are both critically ill and profoundly immunosuppressed will have a complicated clinical course. Opportunistic and nosocomial infections are expected. Disease-related events will be frequent and include:

- Death due to TBM (~40% enrolled participants). Will always be reported as an SAE.
- Disability due to TBM. Will not be reported as an AE.
- TBM-IRIS events and symptoms. Will not be reported as an AE.
- Neurological complications of TBM, including tuberculoma, infarct, seizures, headache due to raised ICP. **Will not be reported as an AE.**
- Other opportunistic infections. Will not be reported as an AE.
- Nosocomial infections, including hospital acquired pneumonias or aspiration pneumonias. Will not be reported as an AE.

Expected disease-related events do not require reporting unless the severity of the event was considered to be unexpected.

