10.2 Planned analyses

The primary outcomes will be CSF and plasma LZD PK parameters, including CSF to plasma ratio, rate of CSF uptake, and plasma absorption rate constant (k_a), drug clearance (Cl/F), volume of distribution (V_d). We will employ a model-based approach using non-linear mixed effects modeling in NONMEM to estimate plasma and CSF PK parameters based on simultaneous analysis of all plasma and CSF drug concentration data.⁷⁴ We will perform post-hoc Bayesian predictions of secondary LZD PK parameters, including C_{max} , time to C_{max} , AUC₀₋₂₄, and elimination half-life in plasma and in CSF. Based on this approach, we will characterize the dynamic uptake of LZD in the CSF when administered with high and standard dose RIF over 4 weeks and derive a dosing algorithm for LZD to achieve target exposures through simulations. Pharmacodynamic breakpoints for LZD against TB are not established, but we will use target AUC₀₋₂₄, AUC/MIC, T>MIC for LZD of 160 µg*hr/mL, 100, and 85%, respectively.^{23,75,76} We will use sparse sampling to estimate the AUC curve based on CSF sampling early, at steady state, and before LZD discontinuation.⁷⁷

For the LZD adverse event evaluation, the primary outcome will be a dichotomous measure of Grade 3 or higher (yes/no) myelosuppression (e.g., anemia, thrombocytopenia, leukopenia) during the 4 weeks of therapy. A secondary outcome will be LZD discontinuation or dose reduction (yes/no) for any AE. We will compare the frequency of myelosuppression between the LZD and no LZD arms across RIF dosing with the Cochran-Mantel-Haenszel test, which accounts for stratified randomization. Within

the LZD arm, we will explore differences in the frequency of myelosuppression between the standard and two high dose RIF arms combined by a chi-square test. We will use an exposure-response model using logistic regression to test if the probability of myelosuppression and LZD discontinuation is related to PK measurements, including C_{min} , C_{max} and AUC₀₋₂₄.

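### Secondary endpoints 1 to 3 in section 2.4 conflict with the outcomes analysed in section 10.2 and, read literally, mix early TBM deaths with linezolid toxicity

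*Combined protocol and SAP*

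**What the plan says.** Objective 2 in section 2.3 is "To determine if LZD exposures in the CSF and plasma predict linezolid AEs". The first three endpoints in section 2.4 are worded differently. The safety endpoint is "Proportion of participants with Grade 3 or higher AEs at 4 weeks", and it makes no mention of drug attribution. The tolerability endpoint that follows is "Proportion of participants who complete LZD treatment", and it carries no rule for a participant who dies first. The endpoint that serves objective 2 is "Exposure-response (PK-PD) relationship, with LZD as predictor and Grade 3 or higher AE as outcome variable", again without any limit to linezolid toxicity.

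Section 10.2 specifies other outcomes. Its main AE outcome is Grade 3 or higher myelosuppression (yes/no) over the 4 weeks. Its tolerability outcome is linezolid stopped or reduced because of an AE. Its exposure-response model is a logistic regression to "test if the probability of myelosuppression and LZD discontinuation is related to PK measurements". It describes no analysis of all Grade 3 or higher AEs and none of completion. The sample size in section 10.1 also rests on myelosuppression.

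The AE rules that bear on the 2.4 wording are these. Section 7.1 counts an event "REGARDLESS of the attribution". Section 7.2 requires recording of "All Grade 3 to 5 AEs" and severity grading of every reported AE. Section 7.4 says: "Death due to TBM (~40% enrolled participants). Will always be reported as an SAE". Most other expected disease-related events listed there are marked as not reportable as AEs; death is not. Section 7.6 states that the AE endpoint is meant to assess linezolid toxicity, and that laboratory abnormalities without symptoms are not reportable AEs unless one of its listed conditions applies.

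**The concern.** Two sections define different outcomes for the same objectives. Nothing says which one answers objectives 1 and 2, so the choice could be made after the data are seen.

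The 2.4 version also fits its own objective poorly. Objective 2 asks about linezolid AEs, but endpoint 3 as worded is any Grade 3 or higher AE. In a disease with high early mortality, that outcome can contain the event that better exposure is hoped to prevent. Toxicity may rise with exposure while death falls, and a composite of the two understates the toxicity relation. Endpoint 2 has the same weakness: a participant who dies on Day 10 while tolerating linezolid well has not completed it.

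The two sections can also diverge in the other direction. A Grade 3 cytopenia without symptoms counts in 10.2, but under 7.6 it need not be an AE for endpoints 1 and 3.

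**Working it through.** **Step 1. Outcomes side by side.**

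| Purpose | Section 2.4 | Section 10.2 |
|---|---|---|
| Safety | any Grade 3+ AE at 4 weeks | Grade 3+ myelosuppression over 4 weeks |
| Tolerability | completion of linezolid | linezolid stopped or reduced for an AE |
| Exposure-response | any Grade 3+ AE | myelosuppression; discontinuation |

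No row agrees. This step needs no assumption.

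**Step 2. Do deaths enter the 2.4 outcomes?** Attribution is not required (7.1), Grades 3 to 5 are recorded and graded (7.2), and TBM death is always an SAE (7.4). A fatal event can hardly be graded below 3. Read literally, a TBM death by Week 4 is an event for endpoints 1 and 3. This is an inference; no sentence says so.

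**Step 3. The plan's own power figure.** Section 10.1 gives at least 80% for 40% against 10%, 30 per arm, alpha 0.05 (two-sided assumed). With a pooled rate of 0.25, the standard errors are √(2 × 0.25 × 0.75/30) = 0.1118 under the null and √((0.24 + 0.09)/30) = 0.1049 under the alternative. Power = Φ((0.30 − 1.96 × 0.1118)/0.1049) = 0.78. A simulated Cochran-Mantel-Haenszel test without continuity correction, over two rifampicin strata, gives 0.80. The stated figure is reproduced.

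**Step 4. Endpoint 1 if deaths count.** Let d be the 4-week death risk, equal in both arms and independent of toxicity (assumed). Event rate = 1 − (1 − toxicity)(1 − d).

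| d | Linezolid | No linezolid | Power, 30 per arm | Share of linezolid-arm events that are deaths without toxicity |
|---|---|---|---|---|
| 10% | 46% | 19% | 0.61 | 13% |
| 20% | 52% | 28% | 0.47 | 23% |
| 30% | 58% | 37% | 0.37 | 31% |
| 40% | 64% | 46% | 0.29 | 38% |

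**Step 5. Endpoint 3 if deaths count.** Take exposure x as standard normal. Toxicity t(x) and death d(x) are logistic in x with fixed marginal rates, independent given x, and the composite is 1 − (1 − t(x))(1 − d(x)). The large-sample logistic odds ratio of the composite per SD, with a true toxicity odds ratio of 2.0 and 20% deaths, is:

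| Toxicity rate | Death unrelated to exposure | Death OR 0.67 per SD |
|---|---|---|
| 40% (planning rate in 10.1) | 1.67 | 1.40 |
| 15% | 1.37 | 1.07 |

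The death rate by Week 4 and both odds ratios are assumptions. The 40% in 10.1 is given without a grade.

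*When it reverses.* With 20% deaths and a death OR of 0.67, the composite OR falls below 1 at 5% toxicity (about 0.84). At 40% toxicity it takes about 40% deaths and a death OR of 0.4 (about 0.9).

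*When death rises with exposure.* With a death OR of 1.5, 40% toxicity and 30% deaths, the composite OR is 1.98, against 1.62 for myelosuppression as observed when death can come first. With no toxicity relation at all (OR 1.0) and 20% deaths, the same formula still gives a composite OR of about 1.17.

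**Step 6. Endpoint 2.** With no intolerance whatever, completion = 1 − d: 90%, 80%, 70% and 60% for d of 10%, 20%, 30% and 40%.

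**The case against.** No sentence says that TBM deaths count in endpoints 1 or 3, or that a death is a failure to complete. The rule in 7.4 governs reporting and does not define an endpoint, and the same section generally waives reporting of expected disease-related events. Section 7.6, the causality assessment in 7.5.3 and the wording of objective 2 all point towards drug toxicity, so an analyst could reasonably set TBM deaths aside. The only exposure-response model for AEs that the plan specifies, in 10.2, does not score deaths as events. All-cause AEs also have a merit in an open-label trial, since they avoid causality judgements. With 30 exposed participants, power is low even for a clean toxicity outcome (about 0.2 to 0.55 across the scenarios tried), so the practical loss is limited.

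Most of this stands. It limits the harm to the endpoints as listed in 2.4 and makes the treatment of deaths unsettled rather than decided. It does not remove the conflict between 2.4 and 10.2. It also leaves 10.2 without a rule for participants who die before they could show toxicity.

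A reader might go further in three ways that the documents do not support:

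- **That completion cannot exceed about 80%.** Section 7.4 gives about 40% deaths with no time span, and section 1.0 places most deaths in the first month in earlier patients, counted from presentation. Any 4-week figure for this trial is an assumption.
- **That the Phase III dose would be chosen wrongly.** Section 10.2 derives the dosing algorithm from PK targets, and no text makes it depend on endpoint 3.
- **That deaths go unreported.** Death is a category of the modified Rankin Scale at 12 and 24 weeks (endpoint 4).

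**Conclusion.** The conflict between 2.4 and 10.2 is plain in the text and should be resolved. As worded, endpoints 1 to 3 do not isolate linezolid toxicity or tolerability, and no rule separates death from intolerance.

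The size depends on assumptions. With 20% dead by Week 4, a true odds ratio of 2.0 per SD appears as about 1.67 or 1.40 at the plan's 40% toxicity rate, and as about 1.37 or 1.07 at 15%. That is dilution, slight to nearly complete.

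A reader might infer that the relation would be reversed. That needs toxicity far below the planning rate, or a strong protective effect of exposure on death that the documents do not quantify. Even in the most extreme scenario tried (25% toxicity, 40% deaths, death OR 0.4), only 7% of simulated 30-participant trials gave a significantly negative slope. If death rises with exposure, the bias runs the other way and the relation looks stronger than observed myelosuppression would show.

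**What to change.** - **Endpoints 1 and 3:** use the 10.2 toxicity outcome, Grade 3 or higher myelosuppression within 4 weeks defined by laboratory value, plus any linezolid toxicities listed in advance. Section 6.3.13 already requires all post-entry laboratory values to be recorded whatever their grade, so the limit in 7.6 need not affect the endpoint.
- **Endpoint 2:** use linezolid discontinuation or dose reduction for an AE, as in 10.2.
- **Section 10.2:** treat death before the event as a competing event for both the toxicity and the discontinuation outcomes. A simple form is three categories at Week 4 (event, death without the event, neither), with exposure-response fitted separately for the event and for death.
- **Supporting lines by arm:** all-cause Grade 3 or higher AEs, completion of linezolid, and deaths by Week 4, each reported separately.

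The cost is a rewording of three items in 2.4 and one paragraph in 10.2, with no new data. The downside is that all-cause Grade 3 or higher AEs become supportive, and any further linezolid toxicities must be listed before the data are seen.

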1.0 BACKGROUND AND STUDY RATIONALE

Although TBM is the most devastating form of TB, it has largely been neglected in the global health research agenda. Even with appropriate therapy up to 50% of patients with TBM die, most within the first month after presentation.¹⁻³ Of those who survive, neurologic disability is common.⁴⁻⁶ Despite these bleak outcomes, a paucity of data exists on the optimal approach to TBM treatment, including for people living with HIV (PLWH).

A targeted approach to TBM management must leverage drugs that penetrate the CNS. In the absence of large-scale trials, the same standard drug regimens and dosing used for pulmonary TB—rifampicin (RIF), isoniazid (INH), pyrazinamide (PZA), and ethambutol (EMB) for two months (intensive therapy), followed by RIF and INH in the continuation phase—are empirically employed for TBM, except with a longer continuation phase to complete 9 to 12 months of therapy. This generic approach assumes that the efficacy of TB drugs is equivalent at all sites of infection, disregarding the unique challenges of infection of the CNS.⁷ Effective drugs for TBM must penetrate the blood brain barrier (BBB) and remain in the CNS to achieve bactericidal drug concentrations.⁸

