6.2.3 Discontinuation Evaluations

Evaluations for Randomized Participants Who Do Not Start Study Treatment

All CRFs must be completed and keyed for the period up to and including the entry visit. Participants who do not start study treatment will be taken off study with no further evaluations required.

Premature Treatment Discontinuation Evaluations

Participants who prematurely discontinue study treatment permanently will have premature discontinuation evaluations performed as noted in Section 6.1 as soon as possible after stopping study treatment, but no later than 14 days after stopping treatment. If the participant discontinues treatment prematurely, the participant will be encouraged to continue on study and receive all evaluations per 6.1 Schedule of Events.

Premature Study Discontinuation Evaluations

Participants who prematurely discontinue participation in the study should have the premature study discontinuation evaluations noted in Section 6.1 performed as soon as possible.

Evaluations for Participants Who Die

All CRFs must be completed and keyed for the period up to the week of death.

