6.3.11 Neurocognitive testing

Neurocognitive testing will be performed as scheduled in 6.1 on individuals who are able to participate. The battery will take approximately 45 minutes to an hour to complete:

Neurocognitive Test Battery

- Wechsler Adult Intelligence Scale-III Digit Symbol (Speed of Information Processing)
- Color Trails 1 (Attention/Working Memory)
- Color Trails 2 (Executive Function)
- Category Fluency (Executive Function)
- Hopkins Verbal Learning Test-Revised or WHO-UCLA Auditory Verbal Learning Test (Verbal Learning and Memory)
- Grooved Pegboard Bilateral, Finger-tapping Bilateral (Fine Motor)

For participants unable to undergo the full test battery, we will attempt to perform the Montreal Cognitive Assessment (MOCA). We will endeavor to have staff assessing neurocognitive and functional outcomes to be blinded to treatment arm.

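### The instrument for the cognitive endpoint depends on post-randomisation ability, with no common score and no value for deaths or untestable survivors, so the linezolid comparison would rest on selected subsets

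*Combined protocol and SAP*

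**What the plan says.** Secondary objective 3 (Section 2.3) is a randomised comparison: "To compare longitudinal neurocognitive and functional outcomes in participants randomized to linezolid versus no LZD for the treatment of TBM". Its cognitive endpoint, item 5 in Section 2.4, is "Montreal Cognitive Assessment (MoCA) or neurocognitive battery performance at 12 and 24 weeks".

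Section 6.3.11 shows what the *or* means in practice. "Neurocognitive testing will be performed as scheduled in 6.1 on individuals who are able to participate", and then: "For participants unable to undergo the full test battery, we will attempt to perform the Montreal Cognitive Assessment (MOCA".

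On deaths, Section 7.4 expects "Death due to TBM (~40% enrolled participants"), and Section 1.0 says that "up to 50% of patients with TBM die, most within the first month after presentation". Section 6.2.3 adds: "All CRFs must be completed and keyed for the period up to the week of death". The functional endpoint in the same list does cover death: "Modified Rankin Scale (death, severe disability, moderately severe, moderate disability, slight disability, no significant disability, no symptoms) at 12 and 24 weeks".

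Section 10.2 plans the PK, myelosuppression, linezolid discontinuation and related exposure-response analyses. It does not mention the cognitive endpoint. No section gives a battery summary score, norms, a conversion between MoCA and the battery, an impairment category common to both, or a rule for deaths and untestable survivors.

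**The concern.** A randomised comparison needs an outcome defined in the same way for everyone randomised. Here the instrument follows the participant's condition at Week 12 or 24, which is itself an outcome of treatment. Comparing battery scores, or MoCA scores, means comparing subsets formed after randomisation.

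The objective is also longitudinal. Someone who manages only MoCA at Week 12 and the battery at Week 24 has no change score on either instrument, so some of those who recover most cannot show it.

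The decision that a participant is unable is not defined. It is made in an open-label trial where blinding of assessors is an aim rather than a requirement (Sections 4.0 and 6.3.11).

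Part of this is a missing analysis, which can be written later. Part is not: MoCA scores never taken from battery participants cannot be recovered by later SAP wording.

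**Working it through.** **1. Which value each participant gets at Week 12 or 24, as the plan is written**

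| Status at visit | Battery | MoCA | Modified Rankin Scale |
|---|---|---|---|
| Dead | none | none | has a category |
| Alive, can do neither test | none | none | has a category |
| Alive, cannot do full battery | not complete | attempted | has a category |
| Alive, can do full battery | yes | not planned | has a category |

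No cognitive column covers more than one complete row; the functional column covers all four.

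**2. Inputs.** 60 participants, 30 with and 30 without linezolid (Section 10.1). Mortality about 40% (Section 7.4) and up to 50% (Section 1.0), with 30% added here as an assumed lower value. Alpha 0.05 and power 80%, borrowed from the myelosuppression statement in Section 10.1; alpha is taken as two-sided because the plan does not say. The plan gives no power, SD or effect size for the cognitive endpoint, so there is no figure of its own to reproduce.

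**3. Survivors per arm**, treating all deaths as occurring before the visit: 30 × (1 − 0.40) = 18. At 30% mortality it is 21, and at 50% it is 15.

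**4. Precision.** Detectable difference in SD units = (1.960 + 0.842) × √(2/n per arm).

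- n = 30: 2.802 × 0.258 = 0.72
- n = 21: 2.802 × 0.309 = 0.86
- n = 18: 2.802 × 0.333 = 0.93
- n = 15: 2.802 × 0.365 = 1.02

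Power for a 0.72 SD difference with 18 per arm is Φ(0.723/0.333 − 1.960) = Φ(0.21), about 58%.

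If 70% of 18 survivors can do the battery (assumed), n = 12.6 and the detectable difference among battery participants is about 1.12 SD. At 50% (n = 9) it is 1.32 SD, and at 90% (n = 16.2) it is 0.98 SD.

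**5. Bias.** Assume that cognition is standard normal and unaffected by linezolid, that it has correlation ρ with a normal liability to survive, and that control mortality is 40%. Mean cognition among survivors at mortality p is ρ × φ(z_p)/(1 − p). The multiplier of ρ is 0.644 at 40%, 0.497 at 30% and 0.350 at 20%. The spurious difference, linezolid minus control, is then:

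- Linezolid mortality 30%: ρ × (0.497 − 0.644), which is −0.04 SD for ρ = 0.3 and −0.10 SD for ρ = 0.7.
- Linezolid mortality 20%: ρ × (0.350 − 0.644), which is −0.09 SD for ρ = 0.3 and −0.21 SD for ρ = 0.7.
- Linezolid mortality 40%: zero.

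Restricting further to those able to do the battery (assumed to be those with latent cognition above −0.5 SD) was simulated with 2,000,000 draws. The shifts were −0.02 to −0.05 SD at 30% mortality and −0.04 to −0.09 SD at 20%. They are smaller because the weakest survivors are already removed from both arms.

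**The case against.** **A sound analysis may still be possible.** The planned data can be ordered as death, untestable, MoCA only, battery, with scores ranked inside each tier. That would use all 60 participants without another test. This stands, so a reader who infers that no sound analysis can be done goes too far. But the ordering is not planned, and it treats inability to do the battery as worse cognition. The battery includes pegboard and finger-tapping tasks (Section 6.3.11), so the reason may be motor.

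**Nothing forbids overlap.** Section 6.3.11 does not prohibit MoCA in battery participants or say that subtests from a partial battery are discarded. This also stands: the lack of a common score is what the plan provides for, not a certainty about what sites will do.

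**Bias is not established.** A reader might infer that the comparison is biased against linezolid, or that a life-saving regimen would look harmful. The documents do not support that. No section excludes deaths or plans a battery-only analysis, and the expected shift is zero if linezolid affects neither survival nor testability. One can build a larger example: with 30 per arm and mortality of 33% versus 50%, there are 20 and 15 survivors, and if the 5 extra survivors score 1 SD lower the shift is 5 × (−1)/20 = −0.25 SD. Both the mortality contrast and the 1 SD gap are assumed. The example also needs one score shared by all survivors, whereas in a battery-only analysis many of those five would be absent.

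**Other endpoints cover part of the ground.** The Modified Rankin Scale includes death and is assessed at the same visits, and the primary PK endpoints are untouched. Both are true. Neither gives the cognitive half of objective 3 a usable outcome.

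**Conclusion.** The point holds as a weakness of one secondary endpoint. As written, the instrument is assigned by post-randomisation ability, no score is common across participants or within a person whose ability changes, and deaths and untestable survivors have no value.

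The loss of precision does not depend on any treatment effect: about 0.93 SD detectable with 18 survivors per arm (0.86 to 1.02 SD for 30% to 50% mortality), against 0.72 SD with 30. The bias is conditional. It is about 0.02 to 0.21 SD against linezolid if linezolid lowers mortality from 40% to 30% or 20%, with the correlations assumed above, and zero with no effect on survival or testability. Set against a detectable difference near 0.93 SD, imprecision is the larger problem. The mortality effects, correlations and testable fractions are assumptions, not figures from the plan.

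The change is worth making before data are collected, because the missing MoCA scores cannot be obtained afterwards.

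**What to change.** - In Section 6.3.11, attempt MoCA in every testable participant at Weeks 12 and 24, before the battery where that is done. Define what counts as unable, and record the reason when a test is not completed.
- In Sections 2.4 and 10.2, name MoCA as the common score for linezolid versus no linezolid. Keep the battery as a supporting analysis in completers.
- Report a ranked analysis of all randomised participants, with death lowest, alive but untestable next, and then MoCA score. Show it alongside survival and the MoCA result in survivors, labelled as a survivor analysis.

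The cost is one short test, already in the protocol, at two existing visits, plus analysis wording. It adds some fatigue ahead of a battery lasting 45 minutes to an hour. The ranked result will partly reflect survival and overlap the Modified Rankin Scale, which is why it should not stand alone. The fix does not restore 30 cognitive scores per arm: the survivor analysis still has at most about 18 per arm at 40% mortality. It does put those survivors on one scale and allows change from Week 12 to Week 24 to be measured.
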